**12.4.9. Source documents**

Source documents provide evidence for the existence of the subject and substantiate the integrity of the data collected. Investigator should maintain a record of the location(s) of their source documents.

**CONFIDENTIAL**209141 (RSV MAT-011)  
Protocol Amendment 6 Final

Data entered in the eCRF that are transcribed from source documents must be consistent with the source documents or the discrepancies must be explained. The investigator may need to request previous medical records or transfer records, depending on the study. Also, current medical records must be available.

Definition of what constitutes source data and source documents can be found in the [glossary of terms](#).

#### **12.4.10. Study and site closure**

GSK or its designee reserves the right to close the study site or terminate the study at any time for any reason at the sole discretion of GSK, provided there is sufficient notice given to account for patient's safe exit from study participation. Study sites regular closure will be upon study completion. A study site is considered closed when all required data/documents and study supplies have been collected and a study-site closure visit has been performed.

The investigator may initiate study-site closure at any time, provided there is reasonable cause and sufficient notice is given in advance of the intended termination.

Reasons for the early closure of a study site by the sponsor or investigator may include but are not limited to:

- Failure of the investigator to comply with the protocol, the requirements of the IRB/IEC or local health authorities, the sponsor's procedures, or GCP guidelines
- Inadequate recruitment of subjects by the investigator
- Discontinuation of further study treatment development

The investigator will:

- Review data collected to ensure accuracy and completeness
- Complete the Study Conclusion screen in the/eCRF.

**CONFIDENTIAL**209141 (RSV MAT-011)  
Protocol Amendment 6 Final**12.5. Appendix 5: Adverse Events: definitions and procedures for recording, evaluating, follow-up, and reporting****12.5.1. Definition of AE****12.5.1.1. AE Definition**

An AE is any untoward medical occurrence in a clinical study subject, temporally associated with the use of a study treatment, whether or not considered related to the study treatment.

NOTE: An AE can therefore be any unfavourable and unintended sign (including an abnormal laboratory finding), symptom, or disease (new or exacerbated) temporally associated with the use of a study treatment.

**12.5.1.2. Events Meeting the AE Definition**

- Significant or unexpected worsening or exacerbation of the condition/indication under study.
- Exacerbation of a chronic or intermittent pre-existing condition including either an increase in frequency and/or intensity of the condition.
- New conditions detected or diagnosed after study vaccine(s) administration even though they may have been present prior to the start of the study.
- Signs, symptoms, or the clinical sequelae of a suspected interaction.
- Signs, symptoms, or the clinical sequelae of a suspected overdose of either study vaccine(s) or a concurrent medication (overdose per se should not be reported as an AE/SAE).
- Signs, symptoms temporally associated with study vaccine(s) administration.
- Significant failure of expected pharmacological or biological action.
- Pre- or post-treatment events that occur as a result of protocol-mandated procedures (i.e. invasive procedures, modification of subject's previous therapeutic regimen).
- Medically attended visits related to adverse events (e.g. Hospital stays, physician visits and emergency room visits).

AEs to be recorded as endpoints (solicited AEs) are described in Section 12.5.3. All other AEs will be recorded as UNSOLICITED AEs.

The signs, symptoms, and/or clinical sequelae resulting from lack of efficacy will be reported as AE or SAE if they fulfil the definition of an AE or SAE.

**CONFIDENTIAL**209141 (RSV MAT-011)  
Protocol Amendment 6 Final**12.5.1.3. Events NOT Meeting the AE Definition**

- Situations where an untoward medical occurrence did not occur (e.g. social and/or convenience admission to a hospital, admission for routine examination).
- Anticipated day-to-day fluctuations of pre-existing disease(s) or condition(s) present or detected at the start of the study that do not worsen.
- Pre-existing conditions or signs and/or symptoms present in a subject prior to the study vaccination. These events will be recorded in the medical history section of the eCRF.

**12.5.2. Definition of SAE**

A SAE is any untoward medical occurrence that:

- a. Results in death,
- b. Is life-threatening,

Note: The term 'life-threatening' in the definition of 'serious' refers to an event in which the subject was at risk of death at the time of the event. It does not refer to an event, which hypothetically might have caused death, had it been more severe.

- c. Requires hospitalisation or prolongation of existing hospitalisation,

Note: In general, hospitalisation signifies that the subject has been admitted at the hospital or emergency ward for observation and/or treatment that would not have been appropriate in the physician's office or in an out-patient setting. Complications that occur during hospitalisation are also considered AEs. If a complication prolongs hospitalisation or fulfils any other serious criteria, the event will also be considered serious. When in doubt as to whether 'hospitalisation' occurred, or was necessary, the AE should be considered serious.

Hospitalisation for elective treatment of a pre-existing condition (known or diagnosed prior to informed consent signature) that did not worsen from baseline is NOT considered an AE.

- d. Results in disability/incapacity, OR

Note: The term disability means a substantial disruption of a person's ability to conduct normal life functions. This definition is not intended to include experiences of relatively minor medical significance such as uncomplicated headache, nausea, vomiting, diarrhoea, influenza like illness, and accidental trauma (e.g. sprained ankle) which may interfere or prevent everyday life functions but do not constitute a substantial disruption.

- e. Is a congenital anomaly/birth defect in the offspring of a study subject.
- f. Medical or scientific judgement should be exercised in deciding whether reporting is appropriate in other situations, such as important medical events that may not be immediately life-threatening or result in death or hospitalisation but may jeopardise the subject or may require medical or surgical intervention to prevent one of the other outcomes listed in the above definition. These should also be considered

**CONFIDENTIAL**209141 (RSV MAT-011)  
Protocol Amendment 6 Final

serious. Examples of such events are invasive or malignant cancers, intensive treatment in an emergency room or at home for allergic bronchospasm, blood dyscrasias or convulsions that do not result in hospitalisation.

### **12.5.3.     Solicited adverse events**

#### **a.     Solicited local (injection-site) adverse events**

The following local (injection-site) AEs will be solicited:

**Table 23     Solicited local adverse events**

Pain at injection site
Redness at injection site
Swelling at injection site

#### **b.     Solicited general adverse events**

The following general AEs will be solicited:

**Table 24     Solicited general adverse events**

Fatigue
Fever
Gastrointestinal symptoms †
Headache

†Gastrointestinal symptoms include nausea, vomiting, diarrhoea and/or abdominal pain.

Note: subjects will be instructed to measure and record the axillary or oral body temperature in the evening. Should additional temperature measurements be performed at other times of day, subjects will be instructed to record the highest temperature in the diary card.

### **12.5.4.     Unsolicited adverse events**

An unsolicited adverse event is an adverse event that was not solicited using a Subject Diary and that was spontaneously communicated by a subjects who has signed the informed consent.

Potential unsolicited AEs may be medically attended (defined as symptoms or illnesses requiring hospitalisation, or emergency room visit, or visit to/by a health care provider), or were of concern to the subjects. In case of such events, subjects will be instructed to contact the site as soon as possible to report the event(s). The detailed information about the reported unsolicited AEs will be collected by the qualified site personnel during the interview and will be documented in the subject's records.

Unsolicited AEs that are not medically attended nor perceived as a concern by subjects will be collected during interview with the subjects and by review of available medical records at the next visit.

**CONFIDENTIAL**209141 (RSV MAT-011)  
Protocol Amendment 6 Final**12.5.5. Clinical laboratory parameters and other abnormal assessments qualifying as adverse events or serious adverse events**

In absence of diagnosis, abnormal laboratory findings (e.g. clinical chemistry, haematology, urinalysis) or other abnormal assessment that are judged by the investigator to be clinically significant will be recorded as AE or SAE if they meet the definition of an AE or SAE (refer to Sections 12.5.1 and 12.5.2). Clinically significant abnormal laboratory findings or other abnormal assessments that are present at baseline and significantly worsen following the start of the study will also be reported as AEs or SAEs. However, clinically significant abnormal laboratory findings or other abnormal assessments that are associated with the disease being studied, unless judged by the investigator as more severe than expected for the subject's condition, or that are present or detected at the start of the study and do not worsen, will not be reported as AEs or SAEs.

The investigator will exercise his or her medical and scientific judgement in deciding whether an abnormal laboratory finding or other abnormal assessment is clinically significant.

**12.5.6. Events or outcomes not qualifying as adverse events or serious adverse events****12.5.6.1. Pregnancy**

Female subjects who become pregnant after the vaccination may continue the study at the discretion of the investigator.

While pregnancy is not considered an AE or SAE, any adverse pregnancy outcome or complication or elective termination of a pregnancy for medical reasons will be recorded and reported as an AE or a SAE.

Note: The pregnancy should always be recorded on an electronic pregnancy report.

The following should always be considered as SAE and will be reported as described in Sections 12.5.8.1 and 12.5.8.4:

- Spontaneous pregnancy loss, including:
  - spontaneous abortion, (spontaneous pregnancy loss before/at 22 weeks of gestation)
  - ectopic and molar pregnancy
  - stillbirth (intrauterine death of foetus after 22 weeks of gestation).

Note: the 22 weeks' cut-off in gestational age is based on WHO-ICD 10 noted in the EMA Guideline on pregnancy exposure [EMA, 2006]. It is recognised that national regulations might be different.

- Any early neonatal death (i.e. death of a live born infant occurring within the first 7 days of life).

**CONFIDENTIAL**209141 (RSV MAT-011)  
Protocol Amendment 6 Final

- Any congenital anomaly or birth defect identified in the offspring of a study subject (either during pregnancy, at birth or later) regardless of whether the foetus is delivered dead or alive. This includes anomalies identified by prenatal ultrasound, amniocentesis or examination of the products of conception after elective or spontaneous abortion.

Furthermore, any SAE occurring as a result of a post-study pregnancy AND considered by the investigator to be reasonably related to the study vaccine(s) will be reported to GSK as described in Section 12.5.8. While the investigator is not obligated to actively seek this information from former subjects, he/she may learn of a pregnancy through spontaneous reporting.

### **12.5.7. Detecting and recording adverse events, serious adverse events and pregnancies**

A Paper Diary (pDiary) hereafter referred to as Subject Diary will be used in this study to capture solicited or unsolicited adverse events. The subject should be trained on how and when to complete each field of the Subject Diary.

The subjects will be instructed to contact the investigator immediately should the subject manifest any signs or symptoms they perceive as serious.

Subject Diary training should be directed at the individual(s) who will perform the measurements of adverse events and who will enter the information into the Subject Diary. This individual may not be the subject, but if a person other than the subject enters information into the Subject Diary, this person's identity must be documented in the Subject Diary. Any individual that makes entries into the Subject Diary must receive training on completion of the Subject Diary at the time of the visit when Subject Diary is dispensed. This training must be documented in the subject's source record.

At the vaccination visit, the diary card will be provided to the subject. The subject/ will be instructed to measure and record the body temperature (oral preferred), and any solicited local/general AEs (i.e. on the day of vaccination and during the next 6 days) or any unsolicited AEs (i.e. on the day of vaccination and during the next 30 days occurring after the 1st and 2nd vaccination. The subject will be instructed to return the completed diary card to the investigator at the next study visit.

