## CONFIDENTIAL

209141 (RSV MAT-011)  
Protocol Amendment 6 Final

Epoch	Epoch 001	Epoch 002 (Vaccination 1)			Epoch 003 (Follow-up 1)		Epoch 004 (Vaccination 2)				Epoch 005 (Follow-up 2)
Type of contact	Screening	Visit 1	Visit 2	Visit 3	Phone Contact 1		Visit 4	Visit 5	Phone Contact 2	Visit 6	Phone Contact 3
Time points	Day -7 to Day 1	Day 1	Day 8	Day 31	Day 181	Day 181 to -7 before 2 nd vaccination	Day -7 to Day of 2 nd vaccination	From 12 up to 18 months post 1 st vaccination	Day 8 post 2 nd vaccination	Day 31 post 2 nd vaccination	Day 181 post 2 nd vaccination
Sampling time points	Pre-Vacc 1	Vacc 1	Post-Vacc 1	Post-Vacc 1	Post-Vacc 1	Pre-Vacc 2	Pre-Vacc 2	Vacc 2	Post-Vacc 2	Post-Vacc 2	Post-Vacc 2
Hematological and biochemical laboratory testing (~5.5 mL)	0						0 				
Blood sampling for humoral immune response (~5 mL) 	•		•	•			•			•	
Study group and treatment number allocation (SBIR)		0									
Treatment number allocation (SBIR)								0			
Vaccine administration		•						•			
Recording of administered treatment number		•						•			
60 minutes post vaccination observation period		0						0			
Training on use of diary cards	0	0						0			
Distribution of diary cards 	0	0						0			
Collection of diary cards		0	0						0		
Diary card transcription by investigator or designate		•	•						•		
Recording of solicited adverse events		•	•					•	•		
Recording of unsolicited adverse events		•	•	•				•	•	•	

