Visit 3: Physical examination will be performed only if deemed necessary by the investigator.

Visit 4: Perform history directed physical exam will be performed and vital signs (blood pressure, heart rate and respiratory rate, temperature) will be recorded in the eCRF. Weight, height and BMI should also be recorded in the eCRF.

Visit 6: Physical examination will be performed only if deemed necessary by the investigator.

3 Only for women of childbearing potential. Urine pregnancy test is sufficient to determine the eligibility to enter the study. Serum pregnancy test (instead of urine test) may be performed if required by country, local or ethics committee regulations.

4 Pre-vaccination vital signs: At Visit 5, the pre-vaccination vital signs (blood pressure, heart rate and respiratory rate, temperature) will be recorded in the eCRF

5 Sub-groups, Method, cut-off, and laboratory locations will be defined in Section [8.4.3](#).

6 Primary Vaccination: The diary card will be distributed at the day of vaccination and will be used for recording solicited and unsolicited AEs, and concomitant medications/products on the day of vaccination and for 6 subsequent days and for recording unsolicited AEs and concomitant medications/products and vaccinations from Day 8 to Day 31.

Second Vaccination: The diary card will be distributed at the day of vaccination and will be used for recording solicited and unsolicited AEs, and concomitant medications/products on the day of vaccination and for 6 subsequent days and for recording unsolicited AEs and concomitant medications/products and vaccinations from Day 8 to Day 31.

7. For Screening and Visit 1 (prior to study vaccine administration), only those SAEs that are considered related to study participation need to be recorded.

8 Recording of Concomitant medications/vaccinations/products will be described in Section [7.5](#)

9 Hematological and biochemical laboratory testing at Visit 4 (D -7 up to and including 2nd dose vaccination) at the investigator's discretion

**CONFIDENTIAL**209141 (RSV MAT-011)  
Protocol Amendment 6 Final

Whenever possible, the investigator should arrange study visits within the intervals described in [Table 4](#).

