**3.3.3. Overall Benefit: Risk conclusion**

The balance of anticipated benefits and apparent risks associated with the RSV maternal (RSVPreF3) vaccine, with *Boostrix*, and with co-administration of the RSV maternal (RSVPreF3) vaccine and *Boostrix* continues to be acceptable following the ongoing systematic review of safety data.

**CONFIDENTIAL**209141 (RSV MAT-011)  
Protocol Amendment 6 Final**4. OBJECTIVE(S) AND ENDPOINT(S)****Table 5 Study objectives and endpoints**

Objectives	Endpoints
Primary (US + ex-US data to be pooled)	
Safety	Safety

 
To evaluate the safety and reactogenicity of 2 dose levels (60 and 120 µg) of RSVPreF3 when given alone or co-administered with dTpa from Vaccination up to Day 31.
 
To evaluate the safety of a 2nd dose of RSVPreF3 given from 12 up to 18 months post 1st Dose up to Day 31 days post 2nd dose vaccination
 
	
 
Occurrence of any Adverse Events (AEs) from Vaccination to Day 31: 
 
Occurrence of each solicited local AEs at the site of injection in both limbs from Vaccination to Day 8;
 
Occurrence of solicited general AEs from Vaccination to Day 8;
 
Occurrence of any unsolicited AEs from Vaccination to Day 31;
 
Occurrence of Serious Adverse Events (SAEs) from Vaccination to Day 31.
 
 
 
Occurrence of any AEs from 2nd dose to Day 31 post-2nd dose vaccination, for all subjects: 
 
Occurrence of each solicited local AE at the site of injection in both deltoids from 2nd dose vaccination to Day 8 post-2nd dose vaccination
 
Occurrence of solicited general AEs from 2nd dose vaccination to Day 8 post 2nd dose vaccination
 
Occurrence of any unsolicited AEs from 2nd dose to Day 31 post- 2nd dose vaccination
 
Occurrence of Serious Adverse Events (SAEs) from 2nd dose vaccination to Day 31 post 2nd dose vaccination.
 
 
 

Immunogenicity	Immunogenicity

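### Dose 1: the diary card must record unsolicited adverse events to Day 31, but Section 12.5.7 has it returned at Visit 2 (Day 8)

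*Protocol*

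**What the plan says.** Four places in the Protocol bear on this.

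- **Section 2, Table 3, footnote 6.** For each vaccination, a card issued on the vaccination day collects solicited and unsolicited events for the first seven days. The same card then serves "for recording unsolicited AEs and concomitant medications/products and vaccinations from Day 8 to Day 31".
- **Section 12.5.7.** The card is given out at the vaccination visit. Unsolicited events are to be entered for the vaccination day and the 30 days after it. The paragraph then ends: "The subject will be instructed to return the completed diary card to the investigator at the next study visit".
- **Section 2, Table 3.** The row "Collection of diary cards" and the row "Diary card transcription by investigator or designate" are both marked, as extracted, at Visit 1, Visit 2 and Phone Contact 2, and at neither Visit 3 nor Visit 6. Distribution is marked at Screening, Visit 1 and Visit 5. The row "Recording of unsolicited adverse events" does include Visit 3 and Visit 6.
- **Section 12.5.4.** Women are told to contact the site promptly about events that are medically attended or that worry them. For the rest: "Unsolicited AEs that are not medically attended nor perceived as a concern by subjects will be collected during interview with the subjects", together with review of available medical records at the next visit.

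The endpoint served is primary. Section 4, Table 5 lists "Occurrence of any unsolicited AEs from Vaccination to Day 31", with a matching endpoint after the second dose. The planned tabulation (Protocol 10.3.4, SAP 5.3.1) uses 30 days: the vaccination day plus 29.

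**The concern.** A card meant to run for 31 days cannot be complete on Day 8. A site that follows the return instruction literally takes the card when about a quarter of the recording period has passed, and nothing in footnote 6 or 12.5.7 provides for giving it back. From then on, minor unsolicited events and medications are captured only if the woman remembers them at Visit 3.

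Recall-based capture tends to miss mild, short-lived events, and those are the events that a diary adds beyond spontaneous reports and record review. A site that instead reads the word completed as the controlling term would leave the card with the woman until Day 31. The two readings give different ascertainment of the same primary endpoint, and the difference would follow centre practice.

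**Working it through.** The plan states no figure on this point, so the check is a day count and a comparison of passages.

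**Inputs**

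- Endpoint window: Day 1 to Day 31, 31 days (Table 5; 12.5.7: vaccination day plus 30).
- Analysis window: Day 1 to Day 30, 30 days (Protocol 10.3.4; SAP 5.3.1).
- First visit after Visit 1: Visit 2, scheduled for Day 8, allowed interval 7 to 10 days (Table 4).
- First visit after Visit 5: Visit 6, scheduled for Day 31 after the second dose. The Day 8 contact in between is a phone call (Table 3).

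**Dose 1.** Days without a collected diary = last day of window − return day + 1, counting the return day as uncovered.

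- Endpoint window: 31 − 8 + 1 = 24; 24/31 = 77%.
- Analysis window: 30 − 8 + 1 = 23; 23/30 = 77%.
- If Visit 2 falls between Day 7 and Day 11 (the 7 to 10 day interval read as day numbers or as elapsed days): 25 down to 21 of 31, or 24 down to 20 of 30.

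**Dose 2.** Under the Section 12.5.7 sentence the card goes back at Visit 6. With return on Day 31, all of Days 1 to 30 are covered: 0 of 30 analysis days are lost.

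**Passages side by side**

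| Source | Dose 1 return | Dose 2 return |
|---|---|---|
| Footnote 6 (recording period) | not before Day 31 | not before Day 31 |
| Section 12.5.7 (next visit) | Visit 2, Day 8 | Visit 6, Day 31 |
| Table 3 as extracted | Visits 1 and 2 | Phone Contact 2 |

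For dose 1, the running text conflicts with itself whatever Table 3 shows. For dose 2, footnote 6 and 12.5.7 agree, and only the extracted table differs.

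**How far Table 3 can be trusted.** The extracted collection row has the card collected on the day it is issued, which makes no sense. Moving the collection and transcription marks one column to the right gives Visit 2, Visit 3 and Visit 6. The superseded schedule in the Amendment 4 log, used here only to judge alignment, also shows dose-2 collection at Visit 6, and the visible Amendment 5 and 6 entries list no change to it. Against a general shift, the unsolicited-event row fits as printed and would not fit if moved. The table marks are therefore uncertain, and the original table must be checked.

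**The case against.** The strongest reply is that this is loose wording. The sentence asks for the completed card, and a card with 30 days still to record is not complete on Day 8, so a sensible site would wait. The original Table 3 may even describe a workable scheme: if the dose-1 diary marks sit one column too far left, cards are issued at Visits 1 and 2 and collected at Visits 2 and 3. Operational detail also sits in the Study Procedures Manual, which is not available here.

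Part of this stands. The table marks cannot carry the point alone. But the text still has one card, issued at vaccination, recording to Day 31, with a return rule that points to Day 8. If Table 3 really shows a two-card scheme, footnote 6 and 12.5.7 do not describe it. Reconciliation is needed on either reading.

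It is also fair that the later days are not unobserved. Unsolicited events are recorded at Visit 3 by interview and record review, medically attended or worrying events are to be reported promptly, and Section 12.5.7.2.1 gives a standard non-leading question. That limits the harm to recall.

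A reader might infer more than the documents support:

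- **That 24 of 31 diary days are lost after each dose.** For dose 2 the return sentence points to Visit 6; only a doubtful table mark points to the phone call.
- **That the two doses are measured differently.** This rests on the same mark. Section 8.1 allows mail or electronic return only in special circumstances, so a phone-call collection would be impractical, but that is a further reason to check the table.
- **That the between-group comparison is biased.** One schedule applies to all observer-blind groups after dose 1, and no differential effect is shown.

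**Conclusion.** The point holds for dose 1. Followed as written, 24 of the 31 endpoint days, or 23 of the 30 analysis days, have no collected diary and rest on interview and record review at Visit 3. The expected effect is some under-reporting of mild unsolicited events and of medications in a primary safety window; its size cannot be estimated from the documents. For dose 2 there is an unresolved text-table conflict and no demonstrated loss.

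The dose-1 counts assume return on Day 8 with no card given back or reissued, which is what the text and the extracted table show. If the original table marks a second card at Visit 2 and collection at Visit 3, the practical loss disappears, and the defect is that footnote 6 and 12.5.7 disagree with the schedule. In either case it should be corrected.

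**What to change.** - **Section 12.5.7:** replace the general return instruction with a named visit per dose: Visit 3 for dose 1 and Visit 6 for dose 2.
- **Visit 2:** review and transcribe the Day 1 to 7 part, then give the card back, or issue a second card for Day 8 onward.
- **Table 3:** check the original table. Make the collection and transcription rows show final collection at Visit 3 and Visit 6, and add distribution at Visit 2 if a second card is chosen.
- **Footnote 6:** state whether there is one card or two, in agreement with the above.

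With return on Day 31, Days 1 to 30 are fully covered after each dose, and at most part of Day 31 is lost from the endpoint window. The cost is wording and table edits, plus printing if a second card is used. All the visits already exist, and no new procedure is needed.
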